- Long-Term Follow-Up:** Follow-up will be conducted at approximately 3, 6, 12, 18, and 24 months (\pm 14 days) after the discontinuation of treatment date. This follow-up will be conducted by telephone contact or standard method used by participating centers and agreed by the Sponsor. This does not require an in-person visit. Information regarding post-trial therapy, survival status, and hematologic malignancy diagnosis will be collected. The long-term follow-up period may end sooner if a participant is diagnosed with a hematologic malignancy or if death is known to have occurred prior to 24 months.
- C1D8 and C1D9:** A +2 day window is allowed for the C1D8 visit. If a window is used for C1D8, the same window should be used for C1D9.
- CXD1:** The start of a new additional cycle should always coincide with the start of trial intervention administration for that cycle. A +3-day window is allowed for the start of new cycles, though cycles should never start early and should be at least 21 days in length. A -2 day window is allowed for the safety assessments scheduled for the CXD1 visit to enable flexibility with visit scheduling.
- CXD8:** Hematology and vital signs to be assessed only on Cycles 2 and 3.
- Molecular Eligibility:** NGS reports will be emailed to the Sponsor-approved central annotation group for central review to confirm molecular eligibility.
- Abbreviated PE:** Starting at Cycle 2, abbreviated PE to be performed every 2 cycles (unless full PE necessary by Investigator judgment).
- Vital Signs:** Blood pressure, heart rate, and temperature to be measured after the participant has been sitting for 5 minutes.
- ECG:** 12-lead ECGs to be done in triplicate \geq 1 minute apart per Table 4 in the study protocol. Participants should be in supine position and resting for at least 10 minutes before trial-related ECGs. For additional cycles, ECG is only to be performed pre-dose on C2D1 and C4D1 and if clinically indicated.

Review of Dosing Diary: Dosing diary will be reviewed at each participant visit and collected at each CXD1 visit and at EOT. Additional details are in the Pharmacy Manual.

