- r. **Paired Biopsies (Arm 1 Only):** Tumor biopsies will be collected during Screening and on C1D17 (+2 days) 1-4 hours post-dose. Participants must have had a minimum of 3 consecutive days of dosing with trial intervention prior to the on-treatment biopsy collection. If biopsy collection at this timepoint is not possible, the Sponsor should be contacted to get approval for collection on an alternative day. Once approved, the participant should have the biopsy as soon as possible after the participant has received at least 3 consecutive days of trial intervention.
- s. **Optional Post-Progression Tumor Biopsy:** An optional tumor biopsy will be requested post-progression for participants with prior confirmed responses or prolonged stable disease to evaluate mechanisms of resistance.
- w. **Tumor Assessment:** Tumor assessments by disease-appropriate standard criteria (RECIST v1.1) using CT/MRI with contrast of known sites of disease as clinically indicated. A baseline tumor assessment must be performed within 28 days of the first dose. Subsequent assessments must be performed every 6 weeks (\pm 7 days) from C1D1 for the first 3 assessments (~5 months/22 weeks on-treatment), or sooner if clinically indicated. Thereafter, assessments must be performed every 9 weeks (\pm 7 days). Per RECIST v1.1, complete response or partial response should be confirmed; tumor imaging for confirmation of response must be performed at least 4 weeks after the first indication of response. The subsequent tumor imaging after the confirmation of response should be obtained per the original scheduled interval from the confirmatory scan (6 weeks \pm 7 days during the first ~5 months of trial treatment or every 9 weeks thereafter). For participants with prostate cancer, radionuclide bone scans will be required at baseline and on the same schedule as the RECIST assessments for the assessment of bone disease per PCWG3 criteria. The appearance of new lesions on a bone scan should be confirmed on a subsequent bone scan before determining disease progression based on these results. If a participant

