12.1.2 Response Evaluation Based on Prostate Cancer Working Group 3 Criteria

The Response Evaluation Criteria in Solid Tumors (RECIST) guidelines (version 1.1) are outlined in Section 12.1.1 and will be utilized for evaluation of response in participants with prostate cancer with measurable and non-measurable disease involving soft tissue lesions. A modification from standard RECIST v1.1 is that bone lesions will not be recorded as target or non-target lesions for the assessment.

In addition to RECIST v1.1, participants with prostate cancer will be evaluated by the Prostate Cancer Working Group (PCWG3) criteria for assessment of bone progression and prostate-specific antigen (PSA) response as described by Scher 2016.

Bone Lesions

The presence or absence of bone metastasis will be assessed at baseline by ^{99m}Tc -methylene diphosphonate radionuclide bone scintigraphy. The total number of bone lesions will be recorded.

Assessment for progression:

- A minimum of two or more new lesions compared with the baseline bone scan after the 12-week flare window.
- If the new lesions occur within the first 12 weeks of treatment, assessment of progression requires a confirmatory scan performed 6 or more weeks later showing two additional new lesions compared with the first follow-up scan to rule out pseudoprogression (2 + 2 rule).
- If at least two additional new lesions are seen on the next (confirmatory) scan performed after the 12-week flare window, the date of progression is the date of the first post-treatment scan, when the first two new lesions were documented.
- Changes in intensity of uptake alone do not constitute either progression or regression.

PSA

For participants with nonmeasurable disease, PSA measurements will be used to assess response. To be evaluable for PSA response PSA levels must be > 2 ng/mL at the most recent assessment and must be rising as determined by a sequence of increasing values at a minimum of 1-week apart prior to treatment start.

Assessment for response:

- Confirmed PSA response is defined as $\geq 50\%$ reduction in PSA from baseline to lowest post-baseline PSA result, with a consecutive assessment conducted at least 3 weeks later.

Assessment for progression:

- PSA progression is defined as a PSA increase $\geq 25\%$ and $\geq 2\text{g/mL}$ above the nadir (or baseline for participants who did not have a decline in PSA), confirmed by a second increasing value at least 3 weeks later.

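### As worded, SAP 12.1.2 lets early bone lesions that failed the 2+2 rule count as progression after week 12; it and footnote w should also state one confirmation rule

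*SAP*

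**What the plan says.** SAP 12.1.2 is the section that sets bone progression: "participants with prostate cancer will be evaluated by the Prostate Cancer Working Group (PCWG3) criteria for assessment of bone progression". Three of its bullets matter here.

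- **Later scans.** Progression is "A minimum of two or more new lesions compared with the baseline bone scan after the 12-week flare window". No confirmatory scan is mentioned.
- **Early lesions.** "If the new lesions occur within the first 12 weeks of treatment, assessment of progression requires a confirmatory scan performed 6 or more weeks later", and that scan must be one "showing two additional new lesions compared with the first follow-up scan to rule out pseudoprogression (2 + 2 rule").
- **Dating.** When at least two further lesions are "seen on the next (confirmatory) scan performed after the 12-week flare window", progression is dated back to the first post-treatment scan. This bullet deals only with lesions first documented on that scan.

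SAP 5.1 defines baseline, unless otherwise noted, as the last non-missing value before the first dose of either drug. Nothing in 12.1.2 resets it for bone scans.

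Footnote w to SAP Table 5 puts bone scans for prostate participants on the RECIST schedule and refers to PCWG3. It then adds: "The appearance of new lesions on a bone scan should be confirmed on a subsequent bone scan before determining disease progression". It gives no time limit. It does not say whether confirming means that the lesions persist or that more appear.

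The same footnote sets scans every 6 weeks "for the first 3 assessments (~5 months/22 weeks on-treatment), or sooner if clinically indicated". "Thereafter, assessments must be performed every 9 weeks". Each scan has a window of 7 days either way.

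**The concern.** The two progression rules in 12.1.2 use different comparators. The 2+2 rule asks what has been added since the first follow-up scan. The later rule asks what is new since before treatment. A flare lesion seen at week 6 that never disappears is still new relative to baseline at week 18. Lesions that the 2+2 rule was written to discount can therefore return through the later rule, with no growth in between.

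The second, smaller point concerns lesions first seen after week 12. A site working from the schedule of activities would wait for another scan. A programmer working from 12.1.2 alone would call progression at once.

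Radiographic progression is one of the stopping reasons in the Protocol synopsis. It also opens the option for Arm 1 participants to move to the combination. A wrong or early call can therefore end monotherapy too soon, and an unconfirmed late case would be classified differently by different readers.

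**Working it through.** The plan gives no figure on this point to reproduce. The check applies the written rules to example lesion histories.

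**Inputs.** The scan schedule and windows come from footnote w, the progression rules from SAP 12.1.2, the definition of baseline from SAP 5.1, and the 21-day cycle from SAP 2.2. The first three scans fall at weeks 6, 12 and 18. The next is at 18 + 9 = week 27.

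**Comparator.** Suppose two new lesions appear at week 6 and persist, and *k* more are first seen at week 18. The week-18 scan is 18 − 6 = 12 weeks after the first follow-up scan, so it meets the minimum of 6 weeks and lies beyond the window.

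- 2+2 is met if *k* ≥ 2.
- The later rule, against baseline, is met if 2 + *k* ≥ 2, which is always true.
- A later rule limited to lesions first seen after the window is met if *k* ≥ 2.

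| k | 2+2 | Later rule vs baseline | Later rule, late lesions only |
|---|---|---|---|
| 0 | no (0 < 2) | yes (2 ≥ 2) | no |
| 1 | no (1 < 2) | yes (3 ≥ 2) | no |
| 2 | yes (2 ≥ 2) | yes (4 ≥ 2) | yes |

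So the two rules disagree for *k* = 0 and *k* = 1. They agree from *k* = 2 upward. Limiting the later rule to late lesions removes the disagreement.

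A mixed case also changes. With one lesion at week 6 and one more at week 18, the baseline count is 1 + 1 = 2, so the current rule is met. Counting late lesions only gives 1, so it is not met.

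**Confirmation.** Suppose two lesions are first seen at week 18 and none before.

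- 12.1.2 read alone: progression is called at week 18.
- Footnote w applied as well: it is called at the next scheduled scan, week 27.
- Difference: 27 − 18 = 9 weeks, or 9 × 7 / 21 = 3 cycles.
- With one week of window on each scan: 9 − 2 = 7 to 9 + 2 = 11 weeks.

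One input is uncertain. Three scans at 6-week intervals end at 3 × 6 = 18 weeks, but the footnote's parenthesis says about 22. If a site kept the 6-week interval until then, the next scan would be at week 24, a gap of 6 weeks (4 to 8 with windows). An unscheduled scan would shorten either gap.

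**The case against.** The strongest reply on the comparator is that the early-lesion bullet is specific and mandatory. It sorts lesions by when they arise and makes a 2+2 scan a requirement for those in the first 12 weeks. Under the usual preference for the specific over the general, such lesions stay under 2+2 for good, and the later rule covers only lesions that arise later. This reading fits the stated aim and may well be what was intended. It is not written, however. The later rule names the baseline scan as comparator and carries no exclusion. A reader might go further and say that 12.1.2 *requires* failed early lesions to be counted. The documents do not support that: the wording allows it, and the early-lesion bullet can be read against it.

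On confirmation, a reader might infer a flat contradiction. That is also too strong. The later rule is silent on confirmation and does not exclude it. Footnote w refers to PCWG3 just before the sentence in question, and 12.1.2 is the PCWG3 section. The two texts can be applied together, so this is a drafting gap. A reader might also conclude that the footnote's sentence should simply be deleted. Nothing in the documents supports dropping late confirmation.

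Finally, the public SAP goes from section 6.6.6 to section 10, and the public Protocol is the synopsis only. A governing rule may stand in the parts not shown. That limits how firmly either point can be put, although the two appendix texts would still read differently to someone using them.

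**Conclusion.** The comparator point holds as a fault of wording. For two persisting week-6 lesions with none or one added by week 18, the written rules give opposite answers on the same scan, and the permissive one defeats the section's own aim. The confirmation point holds as a secondary inconsistency, worth about 9 weeks (7 to 11) in the timing of the call for lesions first seen at week 18. Whether the recorded date moves too depends on a dating convention that the visible text does not give for late lesions.

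The consequence is small. It reaches only prostate participants with bone disease, in a trial of about 52 evaluable participants across four tumour types; the number with prostate cancer is not stated. It bears on the progression date, the decision to stop, and Arm 1 crossover. Treatment past progression is allowed, and crossover also needs eligibility and Medical Monitor approval. A reader might infer that the primary endpoints are compromised. They are not: DLTs and TEAEs are not defined by progression. The only link is indirect, because under SAP 5.2 and 10.2 starting olaparib closes the monotherapy TEAE window.

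The conclusion assumes the literal reading of the later rule, persistence of the early lesions, the nominal scan schedule, and no overriding rule in the non-public sections.

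**What to change.** 1. Reword the later rule in SAP 12.1.2 along these lines: *two or more new lesions first seen after the 12-week flare window; lesions first seen within the window count only through the 2+2 rule.* The sponsor should note that this also settles the mixed case of one early and one late lesion as not yet progression.

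   Changing the later rule's comparator to the first follow-up scan would not do the job. Two lesions first seen at week 12, with none added by week 18, would count as two new lesions against the week-6 scan. Since the 2+2 bullet names that same scan, it is worth saying there which scan is the comparator when early lesions first appear at week 12. The scheduled week-12 scan can fall on days 77 to 91, either side of day 84, so the boundary should be stated in days.

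2. State one confirmation rule for late lesions in both footnote w and 12.1.2. The reading that satisfies both texts is two or more late lesions seen again on the next scheduled scan. Say which scan date is then recorded as progression. If the sponsor prefers no late confirmation, that is a clinical choice to state and justify.

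The cost is a few sentences in the SAP, with no added scans and no change to data collection. If the non-public sections already contain a governing rule, a cross-reference to it from both places may be enough.

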12.1.1 Response Evaluation Criteria in Solid Tumors, Version 1.1

Evaluation of Target Lesions

Complete Response (CR): Disappearance of all target lesions. Any pathological lymph nodes (whether target or non-target) must have reduction in short axis to <10 mm.

Partial Response (PR): At least a 30% decrease in the sum of the diameters of target lesions, taking as reference the baseline sum diameters.

Progressive Disease (PD): At least a 20% increase in the sum of the diameters of target lesions, taking as reference the smallest sum on trial (this includes the baseline sum if that is the smallest on trial). In addition to the relative increase of 20%, the sum must also demonstrate an absolute increase of at least 5 mm. (Note: the appearance of one or more new lesions is also considered progressions).

Stable Disease (SD): Neither sufficient shrinkage to qualify for PR nor sufficient increase to qualify for PD, taking as reference the smallest sum diameters while on trial.

Evaluation of Non-Target Lesions

Complete Response (CR): Disappearance of all non-target lesions and normalization of tumor marker level. All lymph nodes must be non-pathological in size (<10 mm short axis).

Note: If tumor markers are initially above the upper normal limit, they must normalize for a participant to be considered in complete clinical response.

Non-CR/Non-PD: Persistence of one or more non-target lesion(s) and/or maintenance of tumor marker level above the normal limits.

Progressive Disease (PD): Appearance of one or more new lesions and/or unequivocal progression of existing non-target lesions. Unequivocal progression should not normally trump target lesion status. It must be representative of overall disease status change, not a single lesion increase.

Although a clear progression of “non-target” lesions only is exceptional, the opinion of the treating physician should prevail in such circumstances, and the progression status should be confirmed at a later time by the review panel (or Principal Investigator).

Evaluation of Best Overall Response

The best overall response is the best response recorded from the start of the treatment until disease progression/recurrence (taking as reference for PD the smallest measurements recorded since the treatment started). The participant’s best response assignment will depend on the achievement of both measurement and confirmation criteria.

Table 8: For Participants with Measurable Disease (ie, Target Disease)

Target Lesions	Non-Target Lesions	New Lesions	Overall Response	Best Overall Response when Confirmation is Required ^a
CR	CR	No	CR	>4 wks. Confirmation ^b
CR	Non-CR/Non-PD	No	PR	>4 wks. Confirmation ^b
CR	Not evaluated	No	PR	
PR	Non-CR/Non-PD/not evaluated	No	PR	
SD	Non-CR/Non-PD/not evaluated	No	SD	Documented at least once 6 wks. from first dose of trial intervention ^b
PD	Any	Yes or No	PD	No prior SD, PR, or CR
Any	PD ^c	Yes or No	PD	
Any	Any	Yes	PD	

Abbreviations: CR = complete response; PD = progressive disease; PR = partial response; RECIST = Response Evaluation Criteria in Solid Tumors; SD = stable disease

- a. See RECIST v1.1 manuscript for further details on what is evidence of a new lesion.
- b. Only for non-randomized trials with response as primary endpoint.
- c. In exceptional circumstances, unequivocal progression in non-target lesions may be accepted as disease progression.

Note: Participants with a global deterioration of health status requiring discontinuation of treatment without objective evidence of disease progression at that time should be reported as “symptomatic deterioration.” Every effort should be made to document the objective progression even after discontinuation of treatment.

Table 9: For Participants with Non-Measurable Disease (ie, Non-Target Disease)

Non-Target Lesions	New Lesions	Overall Response
CR	No	CR
Non-CR/non-PD	No	Non-CR/non-PD ^a
Not all evaluated	No	not evaluated

Unequivocal PD	Yes or No	PD
Any	Yes	PD

Abbreviations: CR = complete response; PD = progressive disease; SD = stable disease

- a. Non-CR/non-PD' is preferred over 'stable disease' for non-target disease since SD is increasingly used as an endpoint for assessment of efficacy in some studies so to assign this category when no lesions can be measured is not advised.

12.1.2 Response Evaluation Based on Prostate Cancer Working Group 3 Criteria

The Response Evaluation Criteria in Solid Tumors (RECIST) guidelines (version 1.1) are outlined in Section 12.1.1 and will be utilized for evaluation of response in participants with prostate cancer with measurable and non-measurable disease involving soft tissue lesions. A modification from standard RECIST v1.1 is that bone lesions will not be recorded as target or non-target lesions for the assessment.

In addition to RECIST v1.1, participants with prostate cancer will be evaluated by the Prostate Cancer Working Group (PCWG3) criteria for assessment of bone progression and prostate-specific antigen (PSA) response as described by Scher 2016.

Bone Lesions

The presence or absence of bone metastasis will be assessed at baseline by ^{99m}Tc -methylene diphosphonate radionuclide bone scintigraphy. The total number of bone lesions will be recorded.

Assessment for progression:

- A minimum of two or more new lesions compared with the baseline bone scan after the 12-week flare window.
- If the new lesions occur within the first 12 weeks of treatment, assessment of progression requires a confirmatory scan performed 6 or more weeks later showing two additional new lesions compared with the first follow-up scan to rule out pseudoprogression (2 + 2 rule).
- If at least two additional new lesions are seen on the next (confirmatory) scan performed after the 12-week flare window, the date of progression is the date of the first post-treatment scan, when the first two new lesions were documented.
- Changes in intensity of uptake alone do not constitute either progression or regression.

PSA

For participants with nonmeasurable disease, PSA measurements will be used to assess response. To be evaluable for PSA response PSA levels must be > 2 ng/mL at the most recent assessment and must be rising as determined by a sequence of increasing values at a minimum of 1-week apart prior to treatment start.

Assessment for response:

- Confirmed PSA response is defined as $\geq 50\%$ reduction in PSA from baseline to lowest post-baseline PSA result, with a consecutive assessment conducted at least 3 weeks later.

Assessment for progression:

- PSA progression is defined as a PSA increase $\geq 25\%$ and $\geq 2\text{g/mL}$ above the nadir (or baseline for participants who did not have a decline in PSA), confirmed by a second increasing value at least 3 weeks later.
- A PSA rise within the first 12 weeks of therapy in the absence of evidence of confirmed radiologic progression will not be used as a criterion for progression.

12.1.3 Gynecological Cancer Intergroup Definitions for Response and Progression in Participants with Ovarian Cancer

For participants with ovarian cancer with elevated CA-125 levels, response evaluation will include cancer antigen 125 (CA-125) in addition to Response Evaluation Criteria in Solid Tumors (RECIST) v1.1 criteria as per Gynecological Cancer Intergroup (GCIG) criteria (Rustin 2011).

Definition of Response by CA-125

- A $\geq 50\%$ reduction in CA-125 levels from a pretreatment sample. The response must be confirmed and maintained for at least 3 weeks (note that GCIG recommends maintenance for at least 28 days; a modification was made based on the 3-week cycle length in this trial). Participants can be evaluated for a CA-125 response only if they have a pretreatment sample that is at least twice the upper limit of the reference range and within two weeks before starting treatment.
- Intervening samples and the confirmatory sample must be less than or equal to the previous sample (within an assay variability of 10%).
- The date when the CA-125 level is first reduced by 50% is the date of the CA-125 response.
- A CA-125 complete response can occur if CA-125 levels fall to within the reference range.

Definition of Progression by CA-125

- For participants with elevated CA-125 pre-treatment that normalizes or for participants with CA-125 in the normal range at baseline: CA-125 at least 2 times the upper limit of the reference range on 2 occasions at least 1 week apart.
- For participants with elevated CA-125 pre-treatment which never normalizes: CA-125 at least 2 times the nadir value on 2 occasions at least 1 week apart.

- Progressive disease (PD) by objective change in tumor size should always take precedence over changes in CA-125 should it occur first. If measurable disease is reducing in size but the CA125 suggests progression the participant should remain on treatment.
- CA-125 progression will be assigned the date of the first measurement that meets the above criteria.

Note: CA-125 progression in the absence of radiographic or other clinical evidence of progression will not be sufficient criteria for treatment discontinuation in this trial.

Participants are not evaluable by CA-125 if they have received mouse antibodies (unless the assay used has been shown not to be influenced by human antimouse antibody) or if there has been medical and/or surgical interference with their peritoneum or pleura during the previous 28 days.

Evaluation of Best Overall Response by Combined CA-125 and RECIST 1.1 Criteria

- If participants have a CA-125 response but have PD by RECIST within 28 days of the CA-125 response, they will be classified as PD.
- Participants whose best response by RECIST is stable disease (SD) but who have a CA-125 response will be classified as CA-125 responders
- For a participant to be classified as a complete responder according to RECIST, CA-125 levels must be within the normal range

Table 12: For Participants with Measurable Disease

Target Lesion*	Nontarget†	New Lesion	CA 125	Overall Best Response	
CR	CR	No	Normal	CR	Best RECIST 1.1 response for
CR	Non-CR Non-PD	No	Not PD	PR	CR and PR also requires it to
CR	CR	No	PR but not normal	PR	be confirmed and maintained
CR	NE	No	PR	PR	for at least 28 days if response
PR	Non-PD or NAE	No	Not PD	PR	is primary end point
NAE	Non-PD	No	PR	PR	
PD or New >28 days from CA 125 PR‡			PR	PR	
SD§	Non-PD	No	PR	PR	
SD§	Non-PD or NAE	No	Not PR and not PD	SD	
PD or New ≤28 days From CA 125 PR‡			PR	PD	
PD	Any	Yes or No	Any	PD	
Any	PD	Yes or No	Any	PD	
Any	Any	Yes	Any	PD	
Any	Any	Yes or No	PD	PD	

*Target lesions include up to 5 measurable lesions (2 per organ) as defined by RECIST 1.1.

†Nontarget lesions include ascites and peritoneal thickening which are not measurable according to RECIST 1.1.

‡Patients who have a CA 125 response that occurs more than 28 days from PD according to RECIST 1.1 are considered a PR, according to best response, but PD if the RECIST 1.1 PD is within 28 days of CA 125 response.

§The protocol should specify the minimum time interval between 2 measurements for classification as stable disease.

NE, Not evaluated; NAE, not all evaluated.

Table 13: For Participants Without Measurable Disease

CA 125	Nontarget Lesions*	New Lesions	Overall Serological Response	Best Response for This Category Also Requires
Response and Normalized Response	CR	No	CR	Confirmed and maintained for at least 28 days
	Non-PD	No	PR	
Normalized but no response	Non-CR/Non-PD	No	SD	
Non-PR/non-PD	Non-PD	No	SD	
PD	Any	Yes or No	PD	
Any	PD†	Yes or No	PD	
Any	Any	Yes	PD	

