- b. **EOT Visit:** An End-of-Treatment visit will be conducted following the last dose of trial intervention and within +7 days of the discontinuation of treatment date. If a participant comes to the clinic to start a new cycle but the decision is made to discontinue treatment, that visit may be used as the EOT visit. The EOT visit should occur prior to the start of subsequent anticancer treatment.
- c. **Safety Follow-up:** Required for all participants who discontinued from treatment for whatever reason. The window for the Safety Follow-up visit will be 30 (+14) days from the last dose of trial intervention.
- d. **Long-Term Follow-Up:** Follow-up will be conducted at approximately 3, 6, 12, 18, and 24 months (\pm 14 days) after the discontinuation of treatment date. This follow-up will be conducted by telephone contact or standard method used by participating centers and agreed by the Sponsor. This does not require an in-person visit. Information regarding post-trial therapy, survival status, and hematologic malignancy diagnosis will be collected. The Long-term follow-up period may end sooner if a participant is diagnosed with a hematologic malignancy or if death is known to have occurred prior to 24 months.
- e. **C1D8 and C1D9:** A +2 day window is allowed for the C1D8 visit. If a window is used for C1D8, the same window should be used for C1D9.
- f. **CXD1:** The start of a new additional cycle should always coincide with the start of trial intervention administration for that cycle. A +3-day window is allowed for the start of new cycles, though cycles should never start early and should be at least 21 days in length. A -2 day window is allowed for the safety assessments scheduled for the CXD1 visit to enable flexibility with visit scheduling.
- g. **CXD8:** Hematology and vital signs to be assessed only on Cycles 2 and 3.
- h. **Molecular Eligibility:** NGS reports will be emailed to the Sponsor-approved central annotation group for central review to confirm molecular eligibility.
- i. **Abbreviated PE:** Starting at Cycle 2, abbreviated PE to be performed every 2 cycles (unless full PE necessary by Investigator judgment).
- j. **Vital Signs:** Blood pressure, heart rate, and temperature to be measured after the participant has been sitting for 5 minutes.

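### SAP 12.1.2 ties confirmed PSA response to the nadir, so a PSA still falling at the last sample is unconfirmed; it also does not say what the confirming sample must show

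*SAP*

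**What the plan says.** Under SAP section 12.1.2, PSA is the response measure for prostate participants with nonmeasurable disease. They must have PSA above 2 ng/mL and rising before treatment. A confirmed response is a 50% or greater "reduction in PSA from baseline to lowest post-baseline PSA result, with a consecutive assessment conducted at least 3 weeks later". The first part names the value that counts, the nadir. The second part fixes when the other sample is taken and says nothing about its level.

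Two neighbouring rules are more complete:

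- PSA progression, in the same section, must be "confirmed by a second increasing value at least 3 weeks later".
- For CA-125 response, section 12.1.3 says: "The response must be confirmed and maintained for at least 3 weeks". It adds: "Intervening samples and the confirmatory sample must be less than or equal to the previous sample", with a 10% allowance for assay variability. It dates the response at the first 50% fall, not at the nadir.

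The Schedules of Activities (SAP section 12, Tables 5 and 6) place serum tumor markers at screening, on Day 1 of additional cycles and at the end-of-treatment visit. Cycles are 21 days.

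**The concern.** A confirmation rule should separate a lasting fall from a single low reading. This one has two weaknesses.

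First, the nadir is known only in retrospect, and it moves each time PSA falls further. While PSA is still falling, the nadir is the latest sample and nothing follows it. A participant can therefore be unconfirmed after weeks of values well below the 50% line, and a participant already confirmed can lose that status by improving.

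Second, the level of the confirming sample is left open. A programmer who follows the sentence literally would accept any later sample, including one back near baseline.

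At stake is the preliminary activity summary for prostate participants. SAP section 12.1.2 does not record bone lesions as target or non-target, and its bone criteria cover progression only. For bone-only disease, PSA is therefore the only route to response that the section gives. SAP section 11 has clinical activity reviewed descriptively after each cohort, and participants still on treatment at such a review are the ones exposed to the first weakness.

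**Working it through.** The plan states no error rate or sample size for PSA response, so there is no figure to reproduce. The check applies the rule to short PSA series.

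**Inputs**
- Threshold: at least 50% below baseline (SAP 12.1.2).
- Percent change = (value − baseline) / baseline × 100 (SAP 5.1).
- Minimum gap: 3 weeks = 21 days (SAP 12.1.2).
- Sampling on Day 1 of Cycles 2 to 5 with 21-day cycles gives days 22, 43, 64 and 85.
- An end-of-treatment sample can fall less than 21 days after the last cycle sample. One series puts it 7 days later, on day 71.
- The PSA values are invented for illustration.

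**Rules compared**
- *As written:* the nadir is at least 50% down and the next sample is at least 21 days after it, at any level.
- *Half repair:* as written, but that next sample must also be at least 50% down.
- *Full repair:* any value at least 50% down, a later sample at least 21 days after it also at least 50% down, and every sample in between at least 50% down.

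**Arithmetic, baseline 40 (threshold 0.5 × 40 = 20)**
- (18 − 40)/40 = −55%; (15 − 40)/40 = −62.5%; (12 − 40)/40 = −70%.
- (19 − 40)/40 = −52.5%; (36 − 40)/40 = −10%.

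| Baseline | Values (days) | As written | Half repair | Full repair |
|---|---|---|---|---|
| 40 | 24, 18, 15, 12 (22, 43, 64, 85) | not confirmed | not confirmed | confirmed |
| 40 | 24, 18, 19 (22, 43, 64) | confirmed | confirmed | confirmed |
| 40 | 24, 18, 19, 12 (22, 43, 64, 85) | not confirmed | not confirmed | confirmed |
| 100 | 48, 42, 38, 39 (22, 43, 64, 71) | not confirmed | not confirmed | confirmed |
| 40 | 19, 36, 41 (22, 43, 64) | confirmed | not confirmed | not confirmed |
| 100 | 80, 50, 130 (22, 43, 64) | confirmed | not confirmed | not confirmed |
| 100 | 48, 30, 33, 34 (22, 43, 64, 85) | confirmed | confirmed | confirmed |
| 100 | 90, 80, 85 (22, 43, 64) | no response | no response | no response |

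**Reading the table**
- Row 1: PSA is at least 55% down from day 43 to day 85, which is 42 days. The nadir is the day 85 sample, so no later sample exists.
- Rows 2 and 3 are the same participant one cycle apart. A further fall to 12 removes a confirmation already reached.
- Row 4: the nadir is on day 64 and the only later sample is 71 − 64 = 7 days after it. It fails whether the confirming sample must be the next one or may be any later one.
- Rows 5 and 6: the follow-up values are 10% below and 30% above baseline, yet both pass as written.
- Row 7: a sustained fall with a sample at least 3 weeks after its nadir is accepted.
- The half repair removes the transient dips but leaves rows 1, 3 and 4 unconfirmed. The anchor and the value condition both have to change.

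**The case against.** **The rule may be completed elsewhere.** The public SAP body runs from section 6.6.6 to section 10, while its abbreviation list includes objective and composite response rates and duration of response. A fuller derivation may sit in the sections not shown, or in the cited PCWG3 publication, whose confirmation rule the documents do not reproduce. This stands as a limit on certainty. If such a derivation exists, section 12.1.2 should agree with it.

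**The word Confirmed implies a 50% condition.** A reader might infer from the wording that the SAP intends one-off dips to count. The documents do not support that: they are silent on the confirming value and do not waive it, and many readers would supply the condition. The supportable statement is that the value is unstated where the neighbouring rules state theirs. Supplying it does not rescue the nadir anchor, as the half repair shows.

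**Most sustained falls may still be recognised.** A reader might infer that the rule rejects sustained declines in general. It does not. It fails when the nadir is the last sample, or when no adequately spaced sample follows it. For a participant still on treatment, the status may change once a later sample is taken.

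**Visit windows.** A reader might also infer that cycle samples can be 19 days apart and so miss the 3-week gap. The Day 1 column of additional cycles carries a −2 day allowance, but its footnote says: "A -2 day window is allowed for the safety assessments scheduled for the CXD1 visit to enable flexibility with visit scheduling". Serum tumor markers have their own footnote, separate from the safety laboratory tests, and it gives no such window. That inference is not relied on here.

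**Consequence.** The primary endpoints are dose-limiting toxicities and treatment-emergent adverse events, BOIN escalation follows toxicity counts, and the analysis is purely descriptive. This stands and limits the importance of the point.

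**Conclusion.** The concern holds in this limited form. Applied as written, section 12.1.2 leaves a participant with several consecutive values at least 50% below baseline unconfirmed when the nadir is the last sample or the next sample comes under 3 weeks later. This does not depend on how the word Confirmed is read. Separately, the level required of the later sample is not stated, and a literal reading counts a dip followed by a rebound.

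No misclassification rate can be given. The documents provide neither the number of PSA-evaluable prostate participants nor any PSA trajectories, and the series above show only the direction of error. Prostate cancer is one of four tumor types among about 52 evaluable participants, and the protocol admits nonmeasurable disease only by agreement of Sponsor and Investigator. The group is probably small, although in small cohorts one participant can visibly move a reported rate.

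A reader might infer that the activity information used for dose selection is unreliable as a whole. The documents do not support that: the rule affects one descriptive measure, mainly in prostate participants with nonmeasurable disease. The conclusion assumes that no section outside the public text overrides 12.1.2. The change is worth making because it is cheap and the rule is the stated response definition for that group.

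**What to change.** Replace the response definition in SAP 12.1.2 with wording to this effect: *Confirmed PSA response is a PSA at least 50% below baseline at any post-baseline assessment, with a later assessment at least 3 weeks after it also at least 50% below baseline, and any samples between the two also at least 50% below baseline. The response date is the date of the first qualifying value.* Use the nadir only for the best percent change display. Align any derivation in the efficacy sections outside the public text with this definition.

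The cost is SAP wording and a small programming change. PSA is already scheduled on Day 1 of additional cycles and at end of treatment, so no new sampling is needed. The small downside is that transient dips no longer count, so some reported response rates may fall; responders still falling at a data cut would now be counted.
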